7 STUDY SCHEDULE

7.1 Screening

Pre-Vaccination, Screening: Day -14 to Day -1:

- When a potential participant is identified, participants will be provided with a description of the study (purpose and procedures) and asked to read and sign the informed consent. The informed consent will be signed prior to performing any study procedures, including any screening procedures. Demographic information will be collected from the participant.
- After providing written consent for the study, participants will receive a physical exam by a licensed to make medical diagnoses and listed on the Investigator of Record Form as the site principal investigator or sub-investigator. Subjects will have blood pressure, pulse rate, respiration rate and oral temperature recorded. Participants must not eat or drink anything hot or cold, or smoke within 10 minutes prior to taking oral temperature.
- They will have blood work drawn to determine if they are healthy enough for study participation as determined by careful assessment by the study physician as specified in Section 4. For these tests they will have about 2 teaspoons (10 cc) of blood drawn. Safety labs include WBC, Hemoglobin, Hematocrit, Platelet count, PT/INR Potassium and Creatinine. Subjects that would like re-enroll in the study for subsequent second and third years will have the same safety labs and must meet all eligibility criteria. Women of childbearing potential will have a urine pregnancy test and be included if the pregnancy test is negative. The lab test results must be assessed by the study physician using the most current available normal lab ranges and by determining the clinical significance for labs that fall outside of the normal range. The study physician will evaluate the safety labs and will determine if the subject is healthy enough to participate in the study.
- **Medical History:** Medical history will be obtained by interview of the subjects. Subjects will be queried regarding a history of significant medical disorders and a physical examination of the head, eyes, ears, nose throat, mouth, cardiovascular system, lungs, GI tract, nervous system, lymph glands, musculoskeletal system, and skin. will be performed. Medical histories of any allergies, cancer, immunodeficiency, psychiatric illness, substance abuse and autoimmune disease will be solicited by interview of the subjects. Subjects will be asked about any history of allergies.
- **Medications history:** All current medications, prescription and over-the-counter drugs taken in the past month (30 days) will be recorded. All vaccinations received within the past year will be recorded.
- Subjects with transient acute conditions (e.g., local infections, cold and/or flu symptoms, sprains, strains, and associated swelling and bruising) may be asked to return for screening after the transient condition resolves. Subjects

who do not meet inclusion criteria by the second visit will be ineligible for study enrollment.

7.2 Enrollment/Baseline

Day 0- Bone marrow aspiration, vaccination

- Study staff will reconfirm participants' willingness to take part in the study prior to performing any study procedures.
- Women of childbearing potential will have a urine pregnancy test.
- Subjects will have blood pressure, pulse rate, respiration rate and oral temperature recorded. Participants must not eat or drink anything hot or cold, or smoke within 10 minutes prior to taking oral temperature.
- A peripheral blood draw of about 64 ml (4 tablespoon) of blood will be drawn to test baseline antibody levels.

Medical history will be reviewed and updated for any health changes since the screening visit as well as any updates to concomitant medications.

- Eligibility criteria, including results of all clinical screening laboratory evaluations and completion of the eligibility checklist, will be reviewed with participants and by the study staff to assure continued eligibility prior to study enrollment.
- Bone Marrow Aspiration: After having the bone aspirate marrow procedure explained to the subjects and signing the institutional consent for the procedure, the study physician will perform the bone marrow aspiration per institutional standard operating procedure.

Following bone marrow aspiration, the licensed seasonal trivalent inactivated influenza vaccine will be administered according to package insert by an intramuscular injection (shot) into the subject's preferred upper arm (deltoid muscle).

The Impact of COVID-19 on Study Visits:

- Due to the COVID-19 pandemic, all non-essential research was halted in mid-March 2020. New enrollments were placed on hold for this study. Follow-up visits were also halted, which impacted participants' follow-up visits. Participant visits for Day 7 and Day 14 were not impacted. Follow-up visits for Day 28 and Day 90 visits were impacted.
- We are requesting that the windows for the Day 28 visit and the Day 90 visit be extended. Specific details are noted in the Day 28 and Day 90 follow-up visit sections below.
Extending the windows for the Day 28 ad Day 90 follow-up visits would allow samples from participants whose visits were halted at these time points to be collected once the Emory restrictions regarding COVID-19 are lifted and staff can reasonably collect samples, dependent upon when the University and applicable Unit and School allow. The scientists feel that the samples, even if a few months late, will greatly help evaluate the longevity of the responses to flu vaccines.
- Study activities will not be changed, just the timing of the Day 28 and Day 90 visits. However, if a participant does not feel comfortable having a certain

study-related procedure done and declines a particular study-related procedure, they will have the option to do so.

- It is not anticipated that any of the Day 365 visits will be impacted.

Enrollment for this study ended on March 31, 2020.

7.3 Follow-up and Final Visits

- **Day 7 post vaccination study visit:** Subjects will have 64 ml of blood drawn for antibody testing. Vital signs, including oral temperature, blood pressure, pulse rate and respiratory rate will be obtained. A health assessment will be performed including an inquiry about any illness or health change since the last study visit as well as change in concomitant medication. Medical history will be reviewed and updated with any reported changes. An assessment will be made for any adverse events or serious adverse events. The Adverse Event Report Form will be updated if indicated.
- **Day 14 post vaccination study visit (+/- 2 days):** Subjects will have 64 ml of blood drawn for antibody testing. Vital signs including oral temperature, blood pressure, pulse rate and respiratory rate will be obtained. A health assessment will be performed including an inquiry about any illness or health change since the last study visit as well as change in concomitant medication. Medical history will be reviewed and updated with any reported changes. An assessment will be made for any adverse events or serious adverse events. The Adverse Event Report Form will be updated if indicated.

- **Day 28 post vaccination study visit (+/- 2 days):** Subjects will have clinical safety labs drawn including a platelet count and hemoglobin and hematocrit (4ml of blood) Females of childbearing potential will have a urine pregnancy test performed, and the test result must be negative for the subject to continue with study participation. The results of the blood tests must be assessed by the study physician as within a healthy range for continued study participation using the most current normal lab ranges, and evaluated for clinical significance of lab values that fall outside of normal range. Subjects will have 64 ml of blood drawn for antibody testing. Vital signs including oral temperature, blood pressure, pulse rate and respiratory rate will be obtained. A health assessment will be performed including an inquiry about any illness or health change since the last study visit. Concomitant medications will be reviewed and updated. An assessment will be made for any adverse events or serious adverse events. Participants will receive a physical exam by a licensed to make medical diagnoses and listed on the Investigator of Record Form as the site principal investigator or sub-investigator. The Adverse Event Report Form will be updated if indicated. Study eligibility criteria will be reviewed by the study nurse and physician and confirmed that the subject meets all inclusion and none of the exclusion eligibility criteria prior to the bone marrow aspirate procedure. [name] as site principal investigator or the sub-investigator will explain the bone marrow aspirate procedure, and the informed consent document for the procedure will be signed by the subject in the presence of [name]. The bone marrow aspirate procedure and aspirate volume will be the same as the same as at study enrollment.
 - Due to the COVID-19 pandemic, all non-essential research was halted in mid-March 2020.
 - One participant had their Day 28 visit halted.
 - We are requesting that the Day 28 window be extended by a maximum of up to 180 days, to allow completion of the follow-up visit for the impacted participant.
 - The participant will be contacted by phone or via encrypted email message to arrange scheduling of subsequent visits.
 - To assist with assessing symptoms, the COVID-19 Screening Questionnaire/Script will be reviewed with participants prior to bringing the participant in for follow-up visits.
- **Day 90 visit (acceptable range: days 80-120):** Subjects will have 64 ml of blood drawn for antibody testing. Vital signs including oral temperature, blood pressure, pulse rate and respiratory rate will be obtained. A health assessment will be performed including an inquiry about any illness or health change since the last study visit as well as change in concomitant medication. Medical history will be reviewed and updated with any reported changes. An assessment will be made for any adverse events or serious adverse events. The Adverse Event Report Form will be updated based on the subject's self-report.
 - Three participants had their Day 90 visit halted due to the COVID-19 pandemic.
 - We are requesting that the Day 90 window be extended by a maximum of up to 180 days, to allow completion of the follow-up visits for impacted participants.
 - Participants will be contacted by phone or via encrypted email message to arrange scheduling of subsequent visits.
 - To assist with assessing symptoms, the COVID-19 Screening Questionnaire/Script will be reviewed with participants prior to bringing them in for follow-up visits.

- **Day 365 visit (+/- 3 months):** Subjects will have clinical safety labs drawn including a platelet count and hemoglobin and hematocrit (4ml of blood). Females of childbearing potential will have a urine pregnancy test performed, and the test result must be negative for the subject to continue with study participation. The results of the blood tests must be assessed by the study physician to be within a healthy range for continued study participation using the most current normal lab ranges, and evaluated for clinical significance of lab values that fall outside of normal range. Subjects will have 64 ml of blood drawn for antibody testing. Vital signs including oral temperature, blood pressure, pulse rate, and respiratory rate will be obtained. A health assessment will be performed including an inquiry about any illness or health change since the last study visit. Concomitant medications will be reviewed and updated. An assessment will be made for any adverse events or serious adverse events. Participants will receive a physical exam by a licensed to make medical diagnoses and listed on the Investigator of Record Form as the site principal investigator or sub-investigator. The Adverse Event Report Form will be updated if indicated. Study eligibility criteria will be reviewed by the study nurse and physician and confirmed that the subject meets all inclusion and none of the exclusion eligibility

criteria prior to the bone marrow aspirate procedure. [name] will explain the bone marrow aspirate procedure, and the informed consent document for the procedure will be signed by the subject in the presence of [name]. The bone marrow aspirate procedure and aspirate volume will be the same as the as at study enrollment and at visit day 28.

- It is not anticipated that any of the Day 365 visits will be impacted.

The day 365 post vaccination visit will be the final study visit unless the subject decides to re-enroll in the study. Provided eligibility criteria are met, subjects may re-enroll in the study for a total study participation of up to three years per subject. The day 365 visit may also be the day 0 visit for a subject who is re-enrolling into the study, provided that re-screening of the subject occurs and the subject meets study eligibility criteria for continued study participation. These subjects will receive a new study identifier and a separate research record will be maintained by study staff.

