11.2 Sample Size Considerations

A major goal our study is to understand the longevity of plasma cell responses directed against different determinants in the influenza vaccine. Our preliminary data has suggested that plasma cell clonal responses against conserved epitopes may be smaller in number and less prone to persist compared to responses against epitopes which are unique to the particular hemagglutinin strains used in the current year's vaccine. Our deep sequencing data suggests that after one year the frequency of the average vaccine-induced clone in the bone marrow is approximately 33% of the frequency observed at one month. However, there is a large variability in this maintenance (standard deviation of 44%). The small number of cross-reactive clones we have tracked so far have been undetectable after one year, suggesting that their maintenance is substantially lower than the average clone. We wish to be 80% confident in being able to detect whether the maintenance of these cross-reactive clones is at least 3-fold lower than for the average clone (i.e. 11% maintenance vs. 33%) with a P-value less than 0.05. This will require the longitudinal tracking of at least 25 broadly cross reactive plasma cell clones in our patient cohort. Our initial data suggests that we should be able to identify a single broadly cross-reactive clonotype in approximately 50% of our donors, meaning that a sample size of 50 donors will be required to follow 25 cross-reactive clonotypes. With our planned sample size of 55 donors, this allows for a potential dropout rate of 10%.

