11.4 Final Analysis Plan

We will use the unpaired Student's t-test to compare the frequencies of strain-specific and broadly cross-reactive clonotypes in the marrow after one year as expressed as a percentage of their frequencies at one month post vaccination. We will also work to develop a multi-phase exponential decay model for plasma cell persistence in the blood and bone marrow over time. We will use ANOVA to evaluate the contributions of antibody specificity (head vs. stem specific; broadly reactive versus strain specific reactivity), affinity for antigen, and level of hypermutation on the observed exponential decay constants of individual clones in each decline phase that we identify through our modeling. This work will be performed in collaboration with the Emory/UGA CEIRS Data Management Team headed by [name] using the approved Data Management Plan for this contract.

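### The one-year/one-month persistence test makes no allowance for actual sampling day, though Day 365 visits may fall on about Days 275–455 and one Day 28 sample near Day 210

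*Combined protocol and SAP*

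**What the plan says.** - **Analysis.** Section 11.4 compares strain-specific and broadly cross-reactive clonotypes by unpaired t-test on their frequencies "in the marrow after one year as expressed as a percentage of their frequencies at one month post vaccination". It gives no adjustment for sampling day, no analysis window and no rule for late samples. The same section plans a multi-phase exponential decay model, and Section 11 plans mixed models across time points. Neither says whether time is the actual or the nominal day.
- **Day 365.** Section 7.3 sets the window for every participant: "Day 365 visit (+/- 3 months", that is, about Days 275–455.
- **Day 28.** The regular window is ±2 days (Days 26–30). For one participant halted by COVID-19: "We are requesting that the Day 28 window be extended by a maximum of up to 180 days". The limit is about Day 208 or Day 210, depending on whether 180 days are counted from Day 28 or Day 30.
- **Day 90.** The regular range is Days 80–120. For three halted participants: "We are requesting that the Day 90 window be extended by a maximum of up to 180 days", which gives Day 270 or Day 300 on the same two readings.
- **Outcomes tied to these visits.** Section 3.2.1 defines seroconversion by the Day 28 HAI titer, and asks what share of seroconverters still hold a titer of at least 1:40 at about one year. Marrow is taken on Days 0, 28 and 365 only (Protocol Summary schematic; Section 8.2).
- **Dates.** Section 8.2.1 states that samples carry a draw date.

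**The concern.** Longevity is the primary objective, so elapsed time is the main explanatory variable. The ratio in Section 11.4 treats every pair of marrow samples as if it spanned the same interval. Under the windows in Section 7.3, a regular pair can be about 245 to 429 days apart (Day 30 to 275, or Day 26 to 455). For the one participant with an extended Day 28 visit it could be as short as 65 days (Day 210 to 275).

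Two clones that decay identically can then show different persistence because their donors came back at different times. The size of the three-fold contrast on which the study is planned also depends on when people return. If the late Day 28 visit counts as Day 28, its marrow becomes the one-month denominator and its HAI titer decides that participant's seroconversion.

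**Working it through.** **Inputs (Section 11.2).** Maintenance of 33% for the average clone and 11% for cross-reactive clones ("i.e. 11% maintenance vs. 33", in percent), SD 44 points ("standard deviation of 44"), power 80% ("We wish to be 80% confident in being able to detect") and alpha 0.05 ("with a P-value less than 0.05", sidedness not stated).

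**1. The plan's own figure.** The stated 25 clones reproduces as a one-sided comparison with a fixed mean: (44 × (1.645 + 0.842) / 22)² = 24.7, rounded up to 25. Donors: 25 / 0.5 = 50, and 55 × 0.9 = 49.5. A two-sided unpaired test with equal groups would need 63 clones per group. That is a separate matter, and I use the 25-clone variant only as a base for step 4.

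**2. Single-exponential decay (my assumption).** From Day 28 to Day 365 is 337 days.
- k(average) = ln(1/0.33) / 337 = 0.00329 per day (half-life 211 days).
- k(cross-reactive) = ln(1/0.11) / 337 = 0.00655 per day (half-life 106 days).
- Expected ratio = exp(−k × (second day − first day)).

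| First day | Second day | Interval (days) | Average | Cross-reactive | Contrast |
|---|---|---|---|---|---|
| 28 | 275 | 247 | 44.4% | 19.8% | 2.24-fold |
| 28 | 365 | 337 | 33.0% | 11.0% | 3.00-fold |
| 28 | 455 | 427 | 24.5% | 6.1% | 4.02-fold |
| 210 | 365 | 155 | 60.1% | 36.2% | 1.66-fold |
| 210 | 275 | 65 | 80.7% | 65.3% | 1.24-fold |

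Two identical average clones sampled at opposite ends of the Day 365 window differ 44.4 / 24.5 = 1.81-fold from timing alone.

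**3. Other decay shapes.** Here decay runs to a plateau p, with ratio p + (1 − p) × exp(−k(t − 28)) relative to Day 28. The plateau is chosen to pass through 33% and 11% at Day 365. The half-lives are assumed.

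| Half-life | Contrast, Day 275 to Day 455 | First sample Day 210, second Day 365 |
|---|---|---|
| 30 days | 2.95 to 3.01 | 97.1% vs 89.5% (1.09-fold) |
| 60 days | 2.47 to 3.27 | 82.6% vs 54.3% (1.52-fold) |
| 90 days | 2.11 to 4.09 | 72.7% vs 40.0% (1.82-fold) |

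A quick plateau makes the Day 365 window harmless but makes a late first sample more misleading, because most of the loss has happened before that sample is taken.

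**4. Study-level effect (single-exponential).**
- Day 365 visits spread evenly over Days 275–455: mean ratio = (exp(−247k) − exp(−427k)) / (180k), giving 33.5% vs 11.6%, or 2.87-fold. The spread in timing adds an SD of 5.7 points for the average clone: √(44² + 5.7²) = 44.4 instead of 44.
- One late Day 28 donor, if that donor supplies 1 of 25 cross-reactive and 1 of 50 average clones: (24 × 11 + 36.2) / 25 = 12.0% and (49 × 33 + 60.1) / 50 = 33.5%, or 2.79-fold.
- All visits at one edge: the difference is 24.5 points (Day 275) or 18.4 points (Day 455) instead of 22. Power = Φ(√25 × difference / 44 − 1.645) is 87% or 67% instead of 80%.

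**5. Seroconversion.** One participant of 55 moves a percentage by about 1 / 55 = 1.8 points.

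**The case against.** The strongest reply is that the plan already contains the right tools. A multi-phase decay model and an ANOVA on decay constants work with rates over time, and draw dates are recorded. Section 7.2 keeps the late samples because they inform longevity. Both clone types can come from the same donors on the same days, so timing largely rescales both. All this is fair. It shortens the fix, but it does not cover the t-test, which is the comparison that Section 11.2 sizes and which takes no account of the interval.

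Some stronger readings are tempting, but the documents do not support them:
- *All analyses use nominal visit labels.* The mixed and decay models leave the time variable unstated; they are not shown to use nominal days.
- *The Day 90 extension also distorts persistence.* Day 90 has no marrow sample, so it cannot move the ratio or the three-fold contrast. It affects only blood memory B-cell and serum summaries.
- *Late Day 90 samples are really one-year samples.* Overlap with the Day 365 window (from about Day 275) arises only if the 180 days are counted from Day 120. Counted from Day 90, the limit is Day 270.
- *The extended windows apply generally.* They cover one participant (Day 28) and three (Day 90). The one Day 28 donor may decline procedures (Section 7.2) and has only about a 50% chance of yielding a cross-reactive clonotype (Section 11.2), so the 36% figure may apply to no clone.
- *Persistence is biased upward.* A late first sample or an early Day 365 sample raises the ratio; a late Day 365 sample lowers it.

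**Conclusion.** The point holds for the t-test in Section 11.4. Followed as written, it mixes intervals of very different length without adjustment. Under single-exponential decay through 33% and 11%, one donor's expected ratio moves between 44% and 25% across the Day 365 window, and the contrast between 2.2-fold and 4.0-fold. A first sample at Day 210 gives 60% vs 36%.

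These sizes rest on an assumed decay shape. Section 11.2 gives proportions, not rates; its 11% is a target for detection; and the plan itself expects several phases. With a 30-day half-life to a plateau, the Day 365 window hardly matters (2.95 to 3.01-fold).

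A reader might take 2.2-fold to 4.0-fold as the range for the study's estimate. That would require every visit to fall at the same edge. With an even spread the contrast is about 2.87-fold. Some clustering is plausible, because for re-enrollees the Day 365 visit doubles as the next Day 0 and enrollment opens with vaccine availability (Section 4), but the documents do not show it. This is a cheap improvement, not a threat to the study's conclusions.

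**What to change.** 1. State in Sections 11 and 11.4 that actual days since vaccination are the time variable in the mixed and decay models.
2. Adjust the one-year/one-month comparison for the actual days of both samples, for example by regressing the ratio on clone type with the two sampling days as covariates, centred at Days 28 and 365. Avoid converting each ratio to a per-day log rate. Section 11.2 reports cross-reactive clones that were undetectable at one year; their log rate is undefined, whereas a ratio of zero can stay in the regression.
3. Exclude samples taken outside Days 26–30 from the one-month denominator and from Day 28 seroconversion, and samples taken outside Days 80–120 from Day 90 summaries. Keep them in the longitudinal models at their true day.

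The cost is analysis wording, since draw dates are already recorded. On the protocol's counts of halted visits, at most one participant leaves the Day 28 summaries and three leave the Day 90 summaries. Covariate adjustment is only approximate if decay is strongly curved; the decay model is the place to examine that.
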